Percentage of patients requiring non-invasive mechanical ventilation on Days 4 (± 1), 8 (± 1), 15 (± 1), 30 (± 2), and 60 (± 3).	-Frequencies -Unstratified odds ratio
Total duration of non-invasive mechanical ventilation per patient.	-Summary statistics -U-Mann Whitney
Percentage of patients requiring invasive mechanical ventilation or ECMO on Days 4 (± 1), 8 (± 1), 15 (± 1), 30 (± 2), and 60 (± 3).	-Frequencies -Unstratified odds ratio
Total duration of invasive mechanical ventilation or ECMO per patient.	-Summary statistics -U-Mann Whitney
Percentage of patients requiring admission to ICU on Days 4 (± 1), 8 (± 1), 15 (± 1), 30 (± 2), and 60 (± 3).	-Frequencies -Unstratified odds ratio
Total duration of intensive care unit (ICU) stay.	-Summary statistics -U-Mann Whitney
Time to onset of additional (i.e., not present at baseline) immune-modulating drugs.	-Kaplan-Meier (unstratified) -Cox regression (unstratified)

Endpoints	Analyses
Percentage of patients receiving immune-modulating drugs on Days 1, 4 (± 1), 8 (± 1), 15 (± 1), 30 (± 2), and 60 (± 3).	-Frequencies -Unstratified odds ratio
Time to onset of additional (i.e., not present at baseline) antiviral drugs.	-Kaplan-Meier (unstratified) -Cox regression (unstratified)
Percentage of patients receiving subsequent antiviral drugs (i.e., not present at baseline) on Days 4 (± 1), 8 (± 1), 15 (± 1), 30 (± 2), and 60 (± 3).	-Frequencies -Unstratified odds ratio
Percentage of patients with a new infection by Days 4 (± 1), 8 (± 1), 15 (± 1), 30 (± 2), and 60 (± 3).	-Frequencies -Unstratified odds ratio
Cumulative mortality (all-cause and related to COVID-19) by Days 4 (± 1), 8 (± 1), 15 (± 1), 30 (± 2), and 60 (± 3).	-Frequencies -Unstratified odds ratio
Percentage of patients in each study group who require subsequent admission within 30 days of initial end of hospital care [up to day 60(± 3)], related to either COVID-19 or COVID-19 therapy.	-Frequencies -Unstratified odds ratio
Change respect to Day 1 in the viral load of SARS-CoV-2, measured by RT-PCR, by Days 4 (± 1), 8 (± 1), 15 (± 1), 30 (± 2), and 60 (± 3), in each study group.	-Summary statistics -Univariate test (Fisher exact test or U-Mann Whitney) -Mixed model
Percentage of patients in each study group with undetectable viral load, by Days 4 (± 1), 8 (± 1), 15 (± 1), 30 (± 2), and 60 (± 3).	-Frequencies -Unstratified odds ratio

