8.6.2.1 Full Analysis Set (FAS) Population

All randomised patients who have taken at least 1 dose of study treatment (plitidepsin or control) and have completed follow-up for survival until day 30 (± 2). Patients who die before the end of follow-up period will also be included in the FAS population. FAS population will be analysed according to their randomised treatment arm.

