11.8 Summary of Statistical Tests

All the main characteristics for estimands to fulfill study objectives will be defined as footnotes in each table following a similar structure than primary estimand definition. Below it can be found the endpoints to measure the variable definition and the analysis method to be used. Treatment attribute is maintained as 'participants will be randomised to receive plitidepsin versus control in each group' whereas applicable and sensitivity analyses according populations defined in 8.5 will be calculated. For intercurrent events, while applicable, a treatment-policy strategy as defined for the primary estimand will be followed.

Table 3 Summary of statistical tests

Endpoints	Analyses	Population
Efficacy primary endpoint		
1-month all-cause mortality rate.	-Frequencies	-FAS population
Key secondary endpoint		
Time to confirmed negativisation in SARS-CoV-2 antigen test or RT-PCR Ct > 30.	-Kaplan-Meier (unstratified)	-FAS population

Endpoints	Analyses	Population
Efficacy secondary endpoints		
Time to sustained end of COVID-related hospital care from the time of randomisation. Sustained discharge is defined as no subsequent admission within 30 days of initial end of hospital care [up to day 60 (± 3)], related to either COVID-19 or COVID-19 therapy	-Kaplan-Meier (unstratified)	-FAS population
Time to sustained improvement (defined in Protocol Section 7.1.3) and resolution of selected COVID signs/symptoms (See Protocol Appendix 10 - COVID-19 signs/symptoms checklist).	-Kaplan-Meier (unstratified)	-FAS population
Distribution of patients according to their clinical status by the 11-category WHO Clinical Progression Scale, at Days 4 (± 1), 8 (± 1), 15 (± 1), 30 (± 2), and 60 (± 3) (See Protocol Appendix 1 – 11-Point World Health Organization (WHO) Clinical Progression Scale).	-Frequencies	-FAS population
Percentage of patients requiring oxygen therapy on Days 4 (± 1), 8 (± 1), 15 (± 1), 30 (± 2), and 60 (± 3).	-Frequencies	-FAS population
Time to sustained discontinuation (i.e., at least 7 days) of oxygen supplementation.	-Kaplan-Meier (unstratified)	-FAS population
Safety secondary endpoints		
Treatment-emergent adverse events (TEAEs).	-Frequencies (severity grade by NCI-CTCAE v5)	-As treated population
TEAEs \geq grade 3 according to the National Cancer Institute	-Frequencies	-As treated population

Endpoints	Analyses	Population
[NCI]-Common Terminology Criteria for AEs (CTCAE v.5.0).		

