Adverse events of special interest (AESIs).	-Frequencies (severity grade by NCI-CTCAE v5)	-As treated population
Serious adverse events (SAEs).	-Frequencies (severity grade by NCI-CTCAE v5)	-As treated population
Drug related Serious Adverse Events (i.e., SARs).	-Frequencies (severity grade by NCI-CTCAE v5)	-As treated population
Adverse events leading to treatment discontinuation.	-Frequencies (severity grade by NCI-CTCAE v5)	-As treated population
Deaths (COVID-19-related/all).	-Frequencies	-As treated population
Change respect to baseline in individual study-defined laboratory parameters (See Protocol Section 5.7, 5.8 and 5.9 and Appendix 8 - Clinical Laboratory Analyses).	-Frequencies (severity grade by NCI-CTCAE v5)	-As treated population
Change respect to baseline in individual vital signs (See Protocol Section 5.7, 5.8 and 5.9).	-Frequencies	-As treated population
Other Secondary/Exploratory Endpoints		
Percentage of patients requiring advanced oxygen support on Days 4 (± 1), 8 (± 1), 15 (± 1), 30 (± 2), and 60 (± 3).	-Frequencies	-FAS population
Time to intensification of respiratory support (WHO >5) (See Protocol Appendix 1 – 11-Point World Health Organization (WHO) Clinical Progression Scale).	-Kaplan-Meier (unstratified)	-FAS population
Total duration of advanced oxygen support.	-Summary statistics	-FAS population

Endpoints	Analyses	Population
Percentage of patients requiring high-flow oxygen on Days 4 (± 1), 8 (± 1), 15 (± 1), 30 (± 2), and 60 (± 3).	-Frequencies	-FAS population
Total duration of high-flow oxygen therapy per patient.	-Summary statistics	-FAS population
Percentage of patients requiring non-invasive mechanical ventilation on Days 4 (± 1), 8 (± 1), 15 (± 1), 30 (± 2), and 60 (± 3).	-Frequencies	-FAS population
Total duration of non-invasive mechanical ventilation per patient.	-Summary statistics	-FAS population
Percentage of patients requiring invasive mechanical ventilation or ECMO on Days 4 (± 1), 8 (± 1), 15 (± 1), 30 (± 2), and 60 (± 3).	-Frequencies	-FAS population
Total duration of invasive mechanical ventilation or ECMO per patient.	-Summary statistics	-FAS population
Percentage of patients requiring admission to ICU on Days 4 (± 1), 8 (± 1), 15 (± 1), 30 (± 2), and 60 (± 3).	-Frequencies	-FAS population
Total duration of intensive care unit (ICU) stay.	-Summary statistics	-FAS population
Time to onset of additional (i.e., not present at baseline) immune-modulating drugs.	-Kaplan-Meier (unstratified)	-FAS population

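### Total durations of ICU stay, ventilation and oxygen support are summarised with no rule for death, so an arm with more early deaths can look better

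*SAP*

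**What the plan says.** SAP Table 3 (Section 11.8) lists five duration endpoints among the other secondary/exploratory endpoints: "Total duration of advanced oxygen support", "Total duration of high-flow oxygen therapy per patient", "Total duration of non-invasive mechanical ventilation per patient", "Total duration of invasive mechanical ventilation or ECMO per patient" and "Total duration of intensive care unit (ICU) stay". For each, the only analysis is summary statistics and the population is the FAS. SAP Section 11.0 defines these statistics for continuous variables as median, mean, standard deviation, quartiles, minimum and maximum.

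On the analysis set, SAP Section 8.6.2.1 states: "Patients who die before the end of follow-up period will also be included in the FAS population".

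On intercurrent events, SAP Section 11.8 states: "For intercurrent events, while applicable, a treatment-policy strategy as defined for the primary estimand will be followed". The primary estimand (SAP Section 11.6.1) names two such events, stopping treatment and starting a non-protocol therapy.

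Protocol Section 8.5 has the same five endpoints with summary statistics and a "U-Mann Whitney" comparison. SAP version 3.0, abridged after early closure, drops that test. SAP Section 6.0 says that no formal tests will be presented, but that the descriptive tables are to permit a numerical comparison of the two arms.

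**The concern.** Death ends an ICU stay or a period of ventilation. A short total can therefore mean early recovery or early death, and a mean or median cannot tell the two apart. Mortality is the primary endpoint and the plan hopes for a large difference in it, so the arms may differ in how many stays are cut short in this way. The secondary objectives describe efficacy through the need for these supports (SAP Section 7.3), so shorter durations will be read as better. At stake is a set of tables in which the arm with more early deaths can show the more favourable durations. The note under SAP Table 3 rules out sensitivity outputs, so no planned analysis would correct that reading.

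**Working it through.** The documents give no figure for these endpoints, so there is none to reproduce. The check has two parts: whether any rule covers death, and how far its absence could matter.

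**1. Is there a rule for death?**
- The FAS definition keeps patients who die.
- The treatment-policy default refers back to an estimand that does not name death, and a treatment-policy strategy cannot supply a duration after death.
- SAP Section 9.0 leaves missing values out. It imputes death for some patients whose information is lost before day 28, which concerns vital status and gives no duration to a patient who died.
- SAP Section 11.8 promises estimand footnotes in the tables but fixes none for death.
- The protocol has no rule either.

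**2. Illustration among ICU users.**
- From the documents: mortality of 20% on control and 7.5% on plitidepsin (planning example, Protocol Section 8.1 and SAP Section 8.5).
- Assumed: these rates apply among ICU users, survivors stay 14 days, and deaths occur on ICU day 4.
- Mean stay = (1 − d) × 14 + d × 4, with d the mortality:
  - control: 0.80 × 14 + 0.20 × 4 = 12.0 days
  - plitidepsin: 0.925 × 14 + 0.075 × 4 = 13.25 days
- The arm with fewer deaths looks worse by 1.25 days.
- Days alive and out of ICU to Day 30, with death scored 0, = (1 − d) × (30 − 14):
  - control: 0.80 × 16 = 12.8
  - plitidepsin: 0.925 × 16 = 14.8

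**3. Sensitivity to the timing of death.** Let a share u of FAS patients use ICU in both arms, with all deaths among users, L days of stay in survivors and T ICU days before death. Counting non-users as 0, the mean per FAS patient is d × T + (u − d) × L. The difference, control minus plitidepsin, is (0.20 − 0.075) × (T − L) = 0.125 × (T − L). The documents give none of u, L or T, so a range is shown.

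| L | T | Control minus plitidepsin (days per patient) |
|---|---|---|
| 10 | 5 | −0.63 |
| 15 | 5 | −1.25 |
| 20 | 3 | −2.13 |
| 15 | 15 | 0 |
| 15 | 20 | +0.63 |

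For T of 3 to 5 days and L of 10 to 20 days, the false advantage of the arm with more deaths is 0.6 to 2.1 days per patient. It is zero when deaths come as late as discharges and reverses when they come later.

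**4. Sensitivity to who the extra deaths are.** Suppose the extra deaths are extra ICU users, with surviving users at 10% in both arms, L = 15 and T = 5.
- Mean per FAS patient:
  - control: 0.20 × 5 + 0.10 × 15 = 2.50
  - plitidepsin: 0.075 × 5 + 0.10 × 15 = 1.88, so this ordering is correct
- Mean among users:
  - control: 2.50 / 0.30 = 8.3
  - plitidepsin: 1.875 / 0.175 = 10.7, so this ordering is reversed

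The choice of denominator alone changes the direction, and the SAP does not state it.

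**5. The alternative under step 3.** With u = 0.30 and L = 15, days alive and out of ICU to Day H are (1 − u) × H + (u − d) × (H − L).
- H = 30:
  - control: 0.70 × 30 + 0.10 × 15 = 22.5
  - plitidepsin: 0.70 × 30 + 0.225 × 15 = 24.4
- H = 60:
  - control: 0.70 × 60 + 0.10 × 45 = 46.5
  - plitidepsin: 0.70 × 60 + 0.225 × 45 = 52.1

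T does not enter this formula, so the timing of death cannot turn the ordering round.

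**The case against.** A reader might infer that the arm with more early deaths will look better on these endpoints, against the primary result. The documents do not support that as a rule. Steps 3 and 4 show that it depends on when deaths occur, on whether mortality and ICU need rise together, and on the denominator. Protocol Section 4.2 excludes critically ill patients at entry, so invasive support would normally follow later deterioration and could well be more frequent in the arm with more deaths. SAP Section 8.1 cites exceptional need for high-flow oxygen or ICU in compassionate use. If few patients use a support and non-users count as 0, the median is 0 in both arms.

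A reader might also infer that a misleading test result will be reported. It will not: the Mann-Whitney comparison stands only in the protocol and is not run under SAP version 3.0. Its distortion could also be slight. With u = 0.30, L = 15, T = 5 and non-users at 0, the probability favouring the arm with more deaths is 0.70 × 0.30 + 0.20 × 0.225 + 0.5 × (0.49 + 0.015 + 0.0225) = 0.519, against 0.5 under no difference.

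Safeguards exist too. Thirty-day mortality is the primary endpoint, cumulative mortality to Day 60 is tabulated in the same population, and deaths are listed. No decision rests on the durations.

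All of this limits the weight of the point, but it does not supply the missing rule. A mortality table elsewhere in the report does not show how many of the short stays were deaths, and the SAP still intends the arms to be compared numerically.

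**Conclusion.** The omission is real in both documents: five duration endpoints are summarised in a population that includes patients who die, with no rule for death and none for patients who never used the support. When deaths cut stays short, the arm with more of them can look better. At the planning rates the illustration gives 1.25 days among ICU users, and 0.6 to 2.1 days per FAS patient over the early-death range examined. These sizes rest on assumed stay lengths and times of death, and on the same ICU need in both arms; the documents give none of these. The direction is a tendency under early death, not a certainty. Severity is minor, because the endpoints are exploratory, the analysis is descriptive, and mortality is reported in its own right.

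**What to change.** Keep the five protocol-defined durations, but show each separately for survivors and for patients who died, with the number in each. State in the table footnote whether patients who never used the support count as 0 or are left out.

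Add, for each support, days alive and free of it to Day 30 and to Day 60, with deaths scored 0, and base any numerical comparison of the arms on that measure. Label it as added after unmasking: SAP Section 8.2 dates the decision to unmask to 19 March 2024, and the SAP version is dated 20 March 2024. For that reason it should be an addition. Replacing protocol endpoints at this stage, or keeping durations in survivors only, would go too far; survivor-only durations also select on an outcome that arises after randomisation.

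The cost is small: one derived variable per support at each of the two horizons, plus footnotes. Protocol Section 7.1.4 already records the days on which oxygen and respiratory support start and stop, ICU admission and discharge, and death, up to Day 60. The drawbacks are that the added measure mixes death with duration and is post hoc.

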5.2.3 Study Discontinuation

Study discontinuation occurs when an enrolled patient ceases to participate in the study, regardless of the reason. Patients will remain on study until patient consent withdrawal, death, or the date of study termination (clinical cutoff) established by the Sponsor. The date and reason for study discontinuation will be clearly documented in the medical records of the patient.

If the patient withdraws consent for disclosure of future information, the Sponsor may retain and continue to use any data collected before such a withdrawal of consent. Additionally, patients may request destruction of any samples taken and not tested, and the investigator must document this in the site study records. Refer to the Schedule of Assessments ([Appendix 13](#)) for data to be collected at the time of study discontinuation and follow-up and for any further evaluations that need to be completed.

Reasons for study discontinuation can include, but are not limited to:

- Investigator's decision;
- Patient refusal as reason for discontinuation.

5.2.4 Lost to follow up.

A patient will be considered lost to follow-up if he/she repeatedly fails to return for scheduled visits on Days 8 (± 1), 15 (± 1), 30 (± 2), and 60 (± 3), and is unable to be contacted by the study site.

The following actions must be taken if a patient fails to return to the clinic for a required study visit:

- The site must attempt to contact the patient and reschedule the missed visit as soon as possible, counsel the patient on the importance of maintaining the assigned visit schedule, and ascertain whether or not the patient wishes to and/or should continue in the study.
- In cases in which the patient is deemed lost to follow-up, the investigator or designee must make every effort to regain contact with the patient (where possible, 3 telephone calls and, if necessary, a certified letter to the patient's last known mailing address or local equivalent methods). These contact attempts should be documented in the patient's medical record.

Should the patient continue to be unreachable, he/she will be considered to have withdrawn from the study with a primary reason of lost to follow-up.

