2.0 Change History

Version/Date	Change Log
1.0	Created as new
2.0	Protocol has been updated to correct some errors detected and to implement some changes in response to clarifications requested by different drug agencies from the countries where the NEREIDA study is going to be carried out After IDMC Organizational meeting held on 22Feb23 some requests/clarifications have been also added. After agreement, Bayesian analyses will be performed by another CRO 'Phastar'.
3.0	Due to low recruitment, early study closure has been decided on 23Feb24. Therefore, SAP is abridged to provide the essential results for an abbreviated Clinical Study Report.

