The Follow-up period starts after the end-of-treatment and lasts until the end-of-study.

The End of Study (EOS) is Day 60 (± 3) or date of early study termination unless ongoing SAEs, if applicable.

The End of Trial (EOT) will be when the Last Patient Last Visit (LPLV) has occurred.

All patients will receive the best available care as per applicable local, institutional, national, supranational COVID-19 treatment guidelines.

Patients assigned to the experimental arms will receive, in addition, plitidepsin as a 1-h IV infusion, during Days 1 to 3.

Patients randomised to the control arm may receive a regulatory-approved antiviral treatment in addition to the BSC.

For prevention of infusion-related (i.e., plitidepsin-related) reactions (IRRs), allergic reactions and emesis reactions, administration of premedications is mandatory in the experimental arms.

All consenting patients discontinuing early from the study before the EOS visit should complete the early termination/withdrawal procedures.

Duration of Study Periods:

- Screening period: From the day of ICF signing prior to randomisation).
- Day 1: Date of randomisation. Treatment must be started on the same date.
- Treatment period: from Day 1 to 24 h after the last dose of the antiviral therapy; if no antiviral was given in the control arm, then the treatment period will finish on Day 4, for data management purposes.
- Follow-up period: From the end-of-treatment to end-of-study.
- EOS: Day 60 (± 3) or date of early study termination unless ongoing SAEs, if applicable.
- Overall study duration: 60 (± 3) days since randomisation.
- End of the trial will be when the Last Patient Last Visit (LPLV) has occurred.

Independent Data Monitoring Committee (IDMC):

An IDMC was established to provide study oversight. The IDMC was composed of individuals external not only to the Sponsor but also to the trial managers (including Sponsor's and Contract Research Organisation's [CRO] medical monitors) and study investigators.

Given the decision to terminate the study due to low accrual, the IDMC activity has been discontinued and there will not be distinction between blinded and unblinded procedures.

Study “Stopping rules”

The Sponsor may suspend or terminate the study if:

- New toxicological or pharmacological findings or safety issues that invalidate the earlier positive benefit-risk assessment occur;
- Significant safety concerns, according to the Sponsor’s criteria, arise during the conduct of the study;

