9.0 Conventions and Derivations

Variables reported with different units will be homogenized to standardized variables following the International System of Units (e.g. laboratory tests, biometrical assessments...) unless otherwise specified.

By default, all results will be rounded to one decimal place, except when variables are integer, which will be reported without decimals (e.g., age in years). Percentages for 0 counts will not be presented and 100% values will be presented with no decimal places. For representing p-values four decimals will be selected as default but they could be rounded to fewer decimals if necessary.

Missing values will not be included in the calculation of outputs. Unless otherwise noted, missing data will not be imputed or carried forward.

For patients who discontinue treatment due to adverse events (related or not to study treatment) every effort should be made to remain under study follow-up, anyway, if information is lost before day 28 the conservative value of death will be also imputed.

Patients with no available data for any time-to event efficacy endpoint will be censored at time 0. EOS: Day 60 (± 3) or date of early study termination, if applicable. Patients not yet achieving the time to event endpoint will be censored at the last valid assessment prior to EOS. Efron's method will be used to handle ties.

Assessment windows as specified in the clinical protocol will be respected, see protocol Appendix 13 'Schedule of Assessments and Procedures' for definitions of trial days. Baseline is defined as latest test performed between screening and drug administration.

Change from baseline (%) is defined as: $(\text{test value} - \text{baseline value}) / \text{baseline value} \times 100$.

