Percentage of patients receiving immune-modulating drugs on Days 1, 4 (± 1), 8 (± 1), 15 (± 1), 30 (± 2), and 60 (± 3).	-Frequencies	-FAS population
Time to onset of additional (i.e., not present at baseline) antiviral drugs.	-Kaplan-Meier (unstratified)	-FAS population

Endpoints	Analyses	Population
Percentage of patients receiving subsequent antiviral drugs (i.e., not present at baseline) on Days 4 (± 1), 8 (± 1), 15 (± 1), 30 (± 2), and 60 (± 3).	-Frequencies	-FAS population
Percentage of patients with a new infection by Days 4 (± 1), 8 (± 1), 15 (± 1), 30 (± 2), and 60 (± 3).	-Frequencies	-FAS population
Cumulative mortality (all-cause and related to COVID-19) by Days 4 (± 1), 8 (± 1), 15 (± 1), 30 (± 2), and 60 (± 3).	-Frequencies	-FAS population
Percentage of patients in each study group who require subsequent admission within 30 days of initial end of hospital care [up to day 60(± 3)], related to either COVID-19 or COVID-19 therapy.	-Frequencies	-FAS population
Change respect to Day 1 in the viral load of SARS-CoV-2, measured by RT-PCR, by Days 4 (± 1), 8 (± 1), 15 (± 1), 30 (± 2), and 60 (± 3), in each study group.	-Summary statistics	-FAS population
Percentage of patients in each study group with undetectable viral load, by Days 4 (± 1), 8 (± 1), 15 (± 1), 30 (± 2), and 60 (± 3).	-Frequencies	-FAS population
Time to either undetectable viral load of SARS-CoV-2 or > 2 logs reduction respect to Day 1.	-Kaplan-Meier (unstratified)	-FAS population
Change respect to baseline in inflammatory biomarkers (C-reactive protein [CRP], procalcitonin, lactate dehydrogenase [LDH], ferritin, neutrophil-to-lymphocyte ratio, and multiplex cytokines assay,	-Summary statistics	-FAS population

Endpoints	Analyses	Population
by Day 4 (± 1), 8 (± 1), 15 (± 1) and 30 (± 2) and 60 (± 3).		
Change respect to baseline in individual serological assessments against SARS-CoV-2, by Days 30 (± 2), and 60 (± 3).	-Summary statistics	-FAS population
Change respect to baseline in individual T-cell response against SARS-CoV-2 by Days 30 (± 2), and 60 (± 3).	-Summary statistics	-FAS population
Change respect to baseline to Days 15 (± 1), and 30 (± 2) in chest X-ray findings (Brixia score, centrally assessed) (Protocol Appendix 9 – Brixia Score).	-Summary statistics	-FAS population
Percentage of patients requiring modification of the therapy (drugs, dose or schedule) for the underlying disease.	-Frequencies	-FAS population

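### Day-60 cumulative mortality is planned as a raw frequency, but survival status is assured only to about Day 30; any FAS patient last seen alive in between would bias the rate

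*SAP*

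**What the plan says.** SAP 11.8, Table 3, lists the endpoint "Cumulative mortality (all-cause and related to COVID-19) by Days 4", 8, 15, 30 and 60, with frequencies as the analysis and the FAS as the population.

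SAP 8.6.2.1 admits to the FAS randomised and treated patients who "have completed follow-up for survival until day 30" (±2). It adds: "Patients who die before the end of follow-up period will also be included in the FAS population". Nothing is required between Day 30 and Day 60.

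SAP 8.2 ends a patient's study at Day 60 (±3) "or date of early study termination unless ongoing SAEs, if applicable". Protocol 5.2.3 is similar: "Patients will remain on study until patient consent withdrawal, death, or the date of study termination (clinical cutoff) established by the Sponsor". SAP 2.0 records that "Due to low recruitment, early study closure has been decided on 23Feb24".

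For missing data, SAP 9.0 states: "Missing values will not be included in the calculation of outputs". The same section provides censoring only for time-to-event endpoints. It imputes death only for patients who stop treatment because of adverse events and whose information is lost before Day 28. Neither provision covers a patient alive at Day 30 whose Day-60 status is unknown.

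**The concern.** A frequency needs a numerator and a denominator, and for Day 60 the plan does not settle how an incompletely followed survivor enters either. Known deaths always count. A survivor whose contact ends on, say, Day 35 has no Day-60 value. Read literally, the missing-value rule removes that survivor and keeps the deaths, which pushes the rate up. A programmer could instead divide by the whole FAS, which treats the patient as alive and pushes the rate down if the patient later dies unrecorded. Two competent programmers could therefore report different Day-60 mortality from the same data.

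Day 60 is the last mortality time point in the report. SAP 6.0 drops formal tests but says that the descriptive tables will allow a numerical comparison of the arms. If incomplete follow-up differs between arms, part of any Day-60 difference could come from the handling rule rather than from mortality.

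**Working it through.** The documents state no Day-60 mortality figure, so there is none to reproduce. The check asks whether the gap can arise and then how the three candidate estimators behave.

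**Can it arise?**
- The FAS needs survival follow-up to Day 30 (±2), so possibly only to Day 28 (SAP 8.6.2.1).
- The Day-60 window opens on Day 57 (60 − 3). A patient last seen alive between about Day 30 and Day 57 is in the FAS without a Day-60 status.
- Follow-up can end in that interval through consent withdrawal, a sponsor cut-off or early termination (Protocol 5.2.3; SAP 8.2). A patient randomised within about 60 days before the closure decision had not reached Day 60 when it was taken.
- Protocol 5.2.2 asks that patients who received plitidepsin and then withdraw be followed, where possible, for at least 31 (±3) days after the last dose. With the last dose on Day 3, that is about Day 34 (3 + 31). The section states no matching rule for controls, so unequal truncation is possible.

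**Worked example.** From the documents: 20 patients per arm, and 20% mortality (SAP 8.5), hence 4 deaths by Day 30. Assumed: 4 of the 16 survivors are last seen alive at about Day 35, and 1 of the 12 still followed dies on Day 45.
- Dropped from the denominator: (4 + 1)/(20 − 4) = 5/16 = 31.3%.
- Counted as alive: 5/20 = 25.0%.
- Kaplan-Meier: 1 − (16/20) × (11/12) = 1 − 0.733 = 26.7%.
- Limits if all 4 lived or all 4 died: 5/20 = 25.0% to 9/20 = 45.0%.

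**Range.** Let q be the risk of death from Day 30 to Day 60 among Day-30 survivors, and k the number last seen alive just after Day 30. Both are assumptions, and loss is taken as unrelated to prognosis. With 20 patients and 4 deaths by Day 30:
- true rate, which Kaplan-Meier targets: 1 − (16/20)(1 − q);
- expected known deaths: D = 4 + q(16 − k);
- dropped: D/(20 − k);
- counted alive: D/20.

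| q | k | True / Kaplan-Meier | Dropped | Counted alive |
|---|---|---|---|---|
| 0 | 1 | 20.0% | 21.1% | 20.0% |
| 0 | 4 | 20.0% | 25.0% | 20.0% |
| 0 | 8 | 20.0% | 33.3% | 20.0% |
| 10% | 1 | 28.0% | 28.9% | 27.5% |
| 10% | 4 | 28.0% | 32.5% | 26.0% |
| 10% | 8 | 28.0% | 40.0% | 24.0% |
| 20% | 1 | 36.0% | 36.8% | 35.0% |
| 20% | 4 | 36.0% | 40.0% | 32.0% |
| 20% | 8 | 36.0% | 46.7% | 28.0% |

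For example, q = 10% and k = 4 gives D = 4 + 0.10 × 12 = 5.2, so 5.2/16 = 32.5% and 5.2/20 = 26.0%. With k = 0 all three estimators agree.

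**Days 4 to 30.** FAS membership already requires survival follow-up to Day 30 (±2) or death. Kaplan-Meier at Days 4, 8 and 15 therefore equals the raw proportion, and Day 30 can differ only through the two-day window.

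**The case against.** The strongest reply is that truncation is possible but not shown. Closure was for low recruitment. SAP 8.2 keeps Day 60 as the patient's end of study and the last patient's last visit as the end of the trial, and early leavers are to complete termination procedures. Survival status is scheduled at Day 60 or early termination (Protocol 5.9), and sites must pursue patients who miss visits (Protocol 5.2.4). This stands. A reader might infer that the reported Day-60 rate is already distorted, but no passage reports a patient without Day-60 status.

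The missing-value sentence in SAP 9.0 is also generic, and deaths over the whole FAS is a natural reading of a cumulative count. A reader might take from the example a spurious arm difference of about 6 points: 31.3% against 25.0% in a fully followed arm with the same 5 deaths. The documents do not support that as a finding. It needs the drop-missing reading, an arm of 20 in a trial stopped for low accrual, and an assumed 4 truncated patients. If those patients are counted as alive, the same example gives 25.0% in both arms.

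The consequences are limited too. The endpoint is listed as secondary/exploratory, there are no formal tests, and deaths are also listed by patient and tabulated in the As Treated population. Frequencies were among the analyses that Protocol 8.5 gave for this row, and SAP 11.6 deliberately avoids complex outputs. These points restrict the remedy to Day 60. They do not supply the missing rule. Listings let a reader check individual outcomes, but they do not define the denominator of the tabulated rate.

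**Conclusion.** The point holds for Day 60 only, and conditionally. The plan assures survival status to about Day 30, allows follow-up to end before Day 60, and has no row-specific rule for a survivor in that gap. Its general missing-value rule would overstate Day-60 mortality; counting such patients as alive would understate it if later deaths are missed. The size depends on an unreported number of truncated patients. In the assumed arm of 20, the choice moves the rate between 25.0% and 31.3%, with Kaplan-Meier at 26.7%. If nobody is truncated, there is no effect. Kaplan-Meier itself relies on truncation being unrelated to prognosis, which is more plausible for a sponsor cut-off than for withdrawal.

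The result at stake is a descriptive rate and the comparison of arms that readers will make from it. A reader might extend the concern to the primary Day-30 endpoint or to an error rate. Neither follows: the FAS definition covers Day 30 apart from its window, and the abridged SAP makes no formal test.

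**What to change.** In the cumulative mortality row of SAP Table 3, for the Day-60 time point only:
- Report all-cause mortality by Kaplan-Meier with a 95% CI, censoring at the last date known alive.
- Show by arm the raw deaths and the number with known Day-60 vital status.
- For COVID-19-related death, report cumulative incidence with other deaths as competing events. If that is judged too complex for the abbreviated report, give at minimum the counts with the known-status denominator.
- Keep frequencies for Days 4, 8, 15 and 30.

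The cost is one amended row, a footnote and standard code. Kaplan-Meier is already the SAP's method for its time-to-event endpoints. The day of death is recorded to Day 60 (Protocol 7.1.4), and survival status is a scheduled item in Protocol 5.7 to 5.9. The documents do not name a dedicated last-known-alive field, so that date may have to be derived from the latest dated contact at which the patient was alive. The competing-risks estimate is one extra output.
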